## Synopsis

Protocol Title	A prospective, multi-centered, assessor-blinded clinical performance study to evaluate the sensitivity and specificity of the proposed cell/tissue histopathology image processor cCeLL – Ex vivo (Confocal Fluorescence Endomicroscopy) for intraoperative brain tumor diagnosis.
Sponsor	VPIX Medical Inc.
Sites	Korea University Anam Hospital, Seoul, S. Korea Seoul National University Hospital, Seoul, S. Korea Samsung Medical Center, Seoul, S. Korea, Unity Health- St. Michael's Hospital, Toronto, ON, Canada
Coordinating Investigator	[name] MD M.M.Sc Ph.D Korea University College of Medicine
Study Objective	The purpose of this clinical study is to confirm sensitivity and specificity of the cCeLL – Ex vivo in intraoperative brain tumor diagnosis as compared to analysis with frozen section. 

○ The existing workflow for intraoperative brain tumor diagnosis involves tissue biopsy, processing, analysis and confirmation by a pathologist using a frozen section, and relaying the result back to the surgeon.

○ The current intraoperative diagnosis based on frozen section analysis is time-, resource-, and labor-intensive. The process takes over 40 minutes on average, but may take longer if biopsied specimen is insufficient or requires repeated analysis. Thereby the development of an efficient device that allows intraoperative real-time diagnosis is enforced.

○ The “Digital Biopsy” imaging method, using micro-sized confocal laser endomicroscopy, is an emerging technology that enables intraoperative visualization of real-time high-resolution brain tumor tissue images.

○ Neoplastic brain tissue biopsied from participant will be visualized and images will be captured using cCeLL – Ex vivo. The corresponding biopsy samples will be examined with standard frozen-section analysis (H&E slide), to evaluate the sensitivity and specificity of cCeLL – Ex vivo in the diagnosis of brain tumors. This study will also be able to verify the potential of Confocal Endomicroscopy to replace the current standard frozen-section analysis, in intraoperative brain tumor diagnosis.

Background	Prospective, multi-centered, assessor-blinded, clinical performance study
Study Design	

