Analysis Methods	
Primary Endpoints
 
Comparison of the sensitivity/specificity of cCeLL-Ex vivo reading results, and the sensitivity/specificity of the frozen section reading results in one pathological inquiry for brain tumor tissue
 

• Sensitivity of cCeLL-Ex vivo reading result in 1 patient in pathological inquiry for brain tumor tissue: Probability that PS is positive if CC-H positive

• Specificity of cCeLL-Ex vivo reading result in 1 patient in pathological inquiry for brain tumor tissue: Probability that PS is negative if CC-H is negative

• Sensitivity of frozen section reading results for brain tumor tissue: Probability that FS is positive if PS is positive

• Specificity of frozen section reading results from brain tumor tissue: Probability that PS is negative if FS is negative

 
The ratio of the clinical sensitivity/specificity of a cCeLL Ex-vivo image and the sensitivity/specificity of the frozen section image of 1 patient in the pathological inquiry for the total reading results is presented, respectively. To identify a 95 % bilateral confidence interval for the difference between cCeLL- Ex vivo and the frozen section sensitivity/specificity.
 
The statistical significance of the difference between cCeLL-Ex vivo and the frozen section sensitivity/specificity ratio is tested by the McNemar test.
 
Secondary Endpoints
 

1. Comparison of cCeLL-Ex vivo imaging and reading time with frozen section reading time

i. The cCeLL-Ex vivo imaging time is measured and recorded in minutes from the time the fluorescent dye is applied to the specimen for image acquisition

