	
ii. The cCeLL-Ex vivo reading time by the pathologist is measured and recorded in minutes from the time of capturing the cCeLL-Ex vivo image of each brain tumor to the time of the final reading.
 
iii. The imaging and reading time for frozen section is measured in minutes from the time of resecting the specimen undergoing frozen section in the operating room to the time when the pathology department of each institution obtains a frozen section image and reports the findings.
 
iv. Format: _____ Hours _____ Minutes
 
2. Comparison of cCeLL accuracy of evaluating the tumor types via Ex-vivo imaging with the accuracy using frozen section
 

i. Evaluation of tumor types via cCeLL-Ex vivo images by 1 pathologist : Agreement between the result of CC-H and the result of PS

ii. Evaluation of tumor types via frozen section: Agreement between the result of FS and the result of PS

 
3. cCeLL – Time and number of images required to diagnose Ex vivo imaging
 

i. The number of images required for the pathologist to read the brain tumor cCeLL – Ex vivo image will be measured and averaged.

ii. cCeLL – Ex vivo reading time uses that of secondary endpoint 1.

iii. *Average number of images required for cCeLL – Ex vivo image reading of 1 brain tumor specimen: _____

 
4. Non-diagnostic image
 

i. The total number of cCeLL Ex-vivo images among the images confirmed in the vivo reading, and the proportion of the number of images that cannot be read are stated as a percentage (%).

ii. The number of images that cannot be read is recorded when the reader reads it.

 
5. AUC value
 

i. Based on the results of each endpoint, the sensitivity and false positive rate (1-specificity) are used to draw the ROC (Receiver Operating Characteristic) Curve to evaluate the performance of the diagnosis to distinguish between positive and negative, and the accuracy of the diagnosis is evaluated through the AUC (Area Under the Curve) value obtained from the area below the ROC curve.

--	--

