# 6. Study Procedures

## 6.1 Study Design

Prospective, multi-center, assessor-blinded clinical study. Samples will be paired and compared against the current standard of assessment.

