The secondary endpoints will be summarized via descriptive statistics. No hypothesis testing will be performed for the secondary endpoints.

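### Tumor-type accuracy is labelled a comparison on paired samples, but no paired table, difference or interval is specified, and the two planned percentages do not fix the precision of their difference

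*Combined protocol and SAP*

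**What the plan says.** Section 6.1 sets a paired design: "Samples will be paired and compared against the current standard of assessment". Section 6.2 has every sample assessed with the device and compared against frozen section, with one to three samples per participant.

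In the Synopsis (Analysis Methods), secondary endpoint 2 is headed "Comparison of cCeLL accuracy of evaluating the tumor types via Ex-vivo imaging with the accuracy using frozen section". Two quantities are defined under that heading. For cCeLL it is "Agreement between the result of CC-H and the result of PS". For frozen section it is "Evaluation of tumor types via frozen section: Agreement between the result of FS and the result of PS".

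Secondary endpoint 1 is headed "Comparison of cCeLL-Ex vivo imaging and reading time with frozen section reading time". The cCeLL imaging clock runs "from the time the fluorescent dye is applied to the specimen for image acquisition". The frozen-section clock starts when the specimen is resected in the operating room.

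The end of section 8.3.1 governs all secondary endpoints: "The secondary endpoints will be summarized via descriptive statistics. No hypothesis testing will be performed for the secondary endpoints".

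The primary endpoints are handled differently. The Synopsis asks for a 95% interval for the difference in sensitivity and specificity, and section 8.3.1 gives paired tables, discordant cells and margins.

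The Synopsis objective also contains the sentence "This study will also be able to verify the potential of Confocal Endomicroscopy to replace the current standard frozen-section analysis". Section 3.1 states the purpose as sensitivity and specificity compared with frozen section and does not mention replacement.

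**The concern.** Sensitivity and specificity concern tumor versus non-tumor tissue, and section 8.3.1 ties the agreement threshold to the same two quantities. Tumor type is therefore judged only under secondary endpoint 2. Sections 6.2 and 8.2 treat type as something the samples are meant to show.

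The variance of a paired difference in proportions depends on the discordant cells: samples typed correctly by frozen section alone and by cCeLL alone. Two separate agreement percentages do not reveal those cells. A reader could see a lower figure for cCeLL and be unable to tell whether the data establish a loss. The plan already has the right structure for sensitivity and specificity but does not carry it over to type.

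The plan also sets no common denominator for the two type percentages. Section 8.3.2 keeps samples analyzable by frozen section whether or not cCeLL succeeded, and its both-methods analysis is confined to the primary endpoints.

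**Working it through.** **Inputs.** From the plan: 200 tumor-positive samples (section 5.4), a paired design (6.1) and one to three samples per participant (6.2). The documents give no tumor-type accuracy, discordance or intra-participant correlation, so all values for these are assumptions.

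**1. The plan's nearest figure.** No precision is stated for tumor type. For sensitivity, section 8.3.1 states a probability above 90% that the estimated difference is below 5%, with both sensitivities 90% and n = 200.
- If the methods err independently, discordance is 2 × 0.9 × 0.1 = 0.18. The standard error is √(0.18/200) = 0.030, and Φ(0.05/0.030) = 95.2%.
- At the largest possible discordance, 0.20, the standard error is √(0.20/200) = 0.0316, and the probability is 94.3%.

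The plan's figure is reproduced, but it concerns detection and not type.

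**2. What two percentages allow.** Assume type accuracy of 90% for frozen section and 85% for cCeLL on the same 200 samples. The difference is d = 0.05. Let D be the proportion typed correctly by exactly one method.
- Smallest D: cCeLL is never right where frozen section is wrong, so D = 0.05 (10 samples).
- Independent errors: D = 0.90 × 0.15 + 0.85 × 0.10 = 0.22 (44 samples).
- Largest D: the methods never fail on the same sample, so D = 0.10 + 0.15 = 0.25 (50 samples).

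**3. Interval for the difference.** The 95% half-width is 1.96 × √((D − d²)/n).

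| D | Calculation | Half-width (points) | 95% interval (points) |
|---|---|---|---|
| 0.05 | 1.96 × √(0.0475/200) | 3.0 | 2.0 to 8.0 |
| 0.22 | 1.96 × √(0.2175/200) | 6.5 | -1.5 to 11.5 |
| 0.25 | 1.96 × √(0.2475/200) | 6.9 | -1.9 to 11.9 |

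The interval excludes zero only if D < 0.0025 + 200 × (0.05/1.96)² = 0.133, about 26 discordant samples. That lies well inside the possible range of 10 to 50. With assumed accuracies of 90% and 80%, D runs from 0.10 to 0.30. The interval is then 5.8 to 14.2 or 2.5 to 17.5 points, so it excludes zero either way but the width still varies.

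**4. Several samples per participant.** At D = 0.20 and d = 0.05 the half-width is 6.2 points if samples are independent. With an assumed design effect of 1.5 or 2 it becomes 6.2 × √1.5 ≈ 7.5 or 6.2 × √2 ≈ 8.7 points.

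**5. Denominator.** Suppose frozen section types 180 of 200 correctly (90%), cCeLL is readable on 180 of the 200, and 153 of those are correct. On separate denominators cCeLL scores 153/180 = 85%, a loss of 5 points. With unreadable samples counted as not correct it scores 153/200 = 76.5%, a loss of 13.5 points.

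**6. Time.** For a mean within-sample difference at n = 250 with equal standard deviations (assumed), the half-width is 1.96 × √(2(1 − r)/250) standard deviations. That is 0.175 at within-pair correlation r = 0 and 0.078 at r = 0.8. Pairing helps, but only if the two times measure the same span. Here one clock starts at dye application and the other at resection, and no sum is stated for the separate cCeLL imaging and reading times.

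**The case against.** The strongest reply is that these endpoints are descriptive by design, with formal paired inference reserved for the primary endpoints. An interval for tumor type would change no primary conclusion. Section 8.3.1 rules out tests but not a cross-table or a difference. Both endpoints are headed as comparisons, and section 6.7 has the results of all three modalities collected and compared. The figures above rest on assumed accuracies. A reader could bound the discordance from the two percentages, and an unpaired interval would be too wide, hence conservative, when errors are positively correlated.

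Most of this stands and limits the point. A reader might infer that the trial cannot size the loss or gain against frozen section. That is not so, because subtraction gives the point difference on a common sample set and the paired data will exist. A reader might infer that the plan forbids a comparison. It is only silent on one. A reader might fear that a device typing nothing correctly would go unnoticed. It would show 0% beside the frozen-section figure, and the discordant count would then follow from the two percentages.

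Three things remain. Bounding the discordance can leave the sign of the difference unsettled, as the 90% and 85% case shows. The common sample set that subtraction needs is not specified. And an unpaired interval is not reliably conservative here, because clustering within participants works the other way.

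**Conclusion.** The point holds as an inexpensive improvement to secondary endpoint 2. The plan names a paired comparison and defines only per-method figures, so the precision of the difference is not prespecified and cannot in general be recovered from them. Under assumed accuracies of 90% and 85% with n = 200, the same report is compatible with 2.0 to 8.0 points or -1.9 to 11.9 points. These intervals use a normal approximation and treat samples as independent; clustering would widen them if results within a participant are positively correlated.

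For time, the unequal clock starts come first, since an interval around unlike quantities would mislead.

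A reader might also infer that the trial's objective claims cCeLL can replace frozen section. The documents do not support that reading. The Synopsis sentence speaks of potential, section 3.1 omits it, and its main support is the primary non-inferiority analysis of sensitivity and specificity. Narrowing the sentence is optional.

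**What to change.** **Tumor type (Synopsis, Analysis Methods, secondary endpoint 2).**
- Add the 2x2 table of type correct by CC-H against type correct by frozen section, on a common set of samples positive on permanent section.
- Report the paired difference, frozen section minus cCeLL, with a two-sided 95% interval that allows for one to three samples per participant, for example a bootstrap that resamples participants.
- Use the section 8.3.2 population, count samples unreadable by cCeLL as not correct, and repeat on samples readable by both methods.

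**Time (secondary endpoint 1).** Reconcile the start and stop definitions of the two clocks, then report the within-sample difference with an interval.

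**Optional.** Limit the Synopsis sentence on replacing frozen section to tumor versus non-tumor detection, in line with section 3.1, and let any statement on tumor type rest on the paired interval.

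**Cost.** The tumor-type change takes a few lines of analysis text and a small table from data already collected. No hypothesis test is added, so the descriptive rule in section 8.3.1 stands. Aligning the clocks may require a consistent start timestamp. The optional change narrows the wording of the Synopsis.

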Permanent section	PS	PS															
Frozen Section	FS	PS															

Study Endpoints	

- The probability of interpretation results by the interpreting physician (1 pathologist) being positive given that the reference standards is positive

- The probability of interpretation results by the interpreting physician (1 pathologist) being negative given that the reference standards is negative

 
Primary Endpoint
 
The primary endpoints in this study are the agreement between cCeLL Ex vivo and frozen section, the sensitivity of cCeLL ex vivo and frozen section, and the specificity of cCeLL ex vivo and frozen section. These endpoints will be assessed by a single pathologist in the analysis of tumor tissue.
 
Secondary Endpoints
 

1. Comparison of time taken in tissue scanning, visualization, and interpretation using cCeLL – Ex vivo to time taken in frozen section analysis.

2. Accuracy in determining the tumor type

3. Required image counts for adequate analysis and diagnosis using cCeLL – Ex vivo

4. Non-diagnostic Image

5. AUC value

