## 6.2 Study Assessments and Procedures

There will be up to three (3) tissue sample types assessed for each participant: 1- center-of-tumor, 2- normal tissue (collected from inevitable standard resection), and 3- margin tissue. Depending on each participant's circumstance, the number of sample tissues harvested will differ from minimum of one to maximum of three. All tissue samples will be assessed with the investigative device and compared against frozen section analysis.

1. Samples will be collected from consented participants who have satisfied the eligibility criteria.
2. Tissues will be removed as part of the standard neurosurgical procedure. Normal tissues obtained from inevitable resection during the course of surgery.
3. Collected samples will be processed as follows:
  1. Wash the biopsied tissue with Phosphate Buffered Saline (PBS)
  2. Place the tissue on a glass slide
  3. Apply dye onto the tissue
  4. After 1 minute, wipe on gauze and then scan (i.e., cCeLL imaging) the tissue using Pixecton (probe) connected to cCeLL – Ex vivo
  5. Send the processed tissue to pathology to obtain images in the form for frozen sections analysis (FS)/permanent sections analysis (PS)
4. Image recordings of sample tissue using cCeLL – Ex vivo are taken and the obtained data is stored (CC).
5. cCeLL – Ex vivo image data of the collected samples is sent to the central core.
6. The result of frozen section analysis (FS) will be collected from the pathology department of each site.
7. The result of permanent section analysis (PS) of corresponding paraffin-embedded tissue section (PS) will be collected from the pathology department of each site. PS will serve as a reference standard to the analysis result of CC and FS.
8. An interpreting pathologist will analyze given images (CC) and is not allowed to review the reference standards (PS).
9. The cCeLL – Ex vivo image data will be de-identified such that only the unique reference numbers will be displayed in the images provided, and participant information including participant enrollment number and surgery information will be removed.
10. The types of the images obtained from this procedure are as follows:

cCeLL – Ex vivo will capture image data of a resected tissue, prior to frozen sectioning (FS) and permanent sectioning (PS). The sample is used to evaluate the presence or absence of tumors, and also to evaluate the tumor types.

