## **8. Study Evaluation**

### **8.1 Primary Endpoint**

The primary endpoints in this study are the agreement between cCeLL Ex vivo and frozen section, the sensitivity of cCeLL ex vivo and frozen section, and the specificity of cCeLL ex vivo and frozen section. These endpoints will be assessed by a single pathologist in the analysis of tumor tissue.

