**Agreement Table**

		cC		
FS Results	Agree	DisAgree		
	a	b	a+b	
Disagree	c	d	c+d	
		a+c	b+d	n T

The estimate of agreement is  $p_{AG} = (a+d)/n_T$ . It is desired to test the hypothesis that the agreement is greater than 80%. This is compatible with the expected result that both the sensitivity and the specificity will be about 90%. Thus the hypothesis to be tested is that the agreement is 80% (H0: Null hypothesis) versus the alternative hypothesis that the agreement is greater than 80% (HA: Alternative hypothesis).

$$H_0: \pi_{AG} = 80\% \text{ vs } H_A: \pi_{AG} > 80\%$$

Where  $\pi_{AG}$  is the percent agreement between Frozen Section and cCell. This will be tested utilizing the exact binomial test. Estimates of agreement from the pilot study indicate that the agreement will be greater than 86%. In this study, there will be 250 participants available for analysis for the estimation and testing of agreement. For outcome results, if the agreement is 86%, with the sample size of 250, the probability the estimated agreement will be greater than 80% is greater than 90%. That is,  $P(p_{AG} > 80\%) > 90\%$ .

**Sensitivity Table** – Sensitivity is only calculated when the truth standard is positive for tumor.

Agreement Table with Tumor Truth

		cC		
FS Results	Agree w/Truth	Disagree w/Truth		
	e	f	e+f	
Disagree	g	h	g+h	
		e+g	f+h	n T

The sensitivity of the Frozen Section is given by  $p_{SenF} = (e+f)/n_T$  and the sensitivity of cCell is given by  $p_{SenC} = (e+g)/n_T$ . It is desired to demonstrate that the sensitivity of cCell is non inferior to that of Frozen section.

The non inferiority of the sensitivity of cCell result versus the sensitivity of the Frozen Section is given as:

$$H_0: \pi_{SenF} - \pi_{SenC} > \Delta \text{ versus } H_A: \pi_{SenF} - \pi_{SenC} \leq \Delta$$

Here  $\pi_{SenF}$  is the true sensitivity for Frozen Section and  $\pi_{SenC}$  is the true sensitivity for cCell. The parameter  $\Delta$  is the non-inferiority limit. In this study, it is proposed to utilize a  $\Delta=0.05$  (5%). If that  $\Delta$  is used and the anticipated sensitivity for both Frozen Section and cCell is 90%, then

with a sample size of 200 tumor positive samples the probability the difference between the estimated sensitivities is less than 5% is greater than 90%. That is  $P((\pi_{\text{SenF}} - \pi_{\text{SenC}} \leq 5\%) > 90\%.$

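### As specified, the AUC endpoint rests on one positive/negative read, so it equals (sensitivity + specificity)/2 and is not an area over thresholds

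*Combined protocol and SAP*

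**What the plan says.** Section 8.2 lists secondary endpoint 5 only by name. The one account of how it is computed is in the Synopsis, Analysis Methods, Secondary Endpoints, item 5. There, "the sensitivity and false positive rate (1-specificity) are used to draw the ROC (Receiver Operating Characteristic) Curve". The input is described as "Based on the results of each endpoint", and the stated purpose is "to evaluate the performance of the diagnosis to distinguish between positive and negative".

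The read behind those quantities is described as binary throughout:

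- Under step 10 of the Synopsis study procedure, sensitivity is "The probability of interpretation results by the interpreting physician (1 pathologist) being positive given that the reference standards is positive".
- Specificity, in the same place, is "The probability of interpretation results by the interpreting physician (1 pathologist) being negative given that the reference standards is negative".
- Section 6.2 says of each specimen: "The sample is used to evaluate the presence or absence of tumors, and also to evaluate the tumor types". Tumor type is a nominal result and supplies no tumor/no-tumor threshold.
- Section 8.1 says of the primary endpoints: "These endpoints will be assessed by a single pathologist in the analysis of tumor tissue".
- Section 8.3.1 reduces agreement, sensitivity and specificity to 2x2 tables.

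Section 8.3 contains no ROC method. Section 8.3.1 closes by making the secondary endpoints descriptive, without hypothesis tests. No confidence rating, ordinal scale, continuous device output or varying cut-off appears anywhere in the documents.

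**The concern.** An ROC curve shows how the true and false positive rates move together as the threshold for calling a sample positive is varied. A single dichotomous call has no threshold to vary. It gives one pair of rates, and joining that pair to the two corners of the plot produces a figure with an area, but the area carries no information beyond the pair itself.

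What is at stake is interpretation. The results would contain a value labelled AUC that looks like a further measure of accuracy but is the average of two primary estimates. It would conceal how errors divide between missed tumor and false alarms, and it could be set beside AUCs from graded readings, with which it is not comparable.

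**Working it through.** **Inputs**

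- Sensitivity (Se): Section 8.3.1 states that "the anticipated sensitivity for both Frozen Section and cCell is 90" per cent.
- Specificity (Sp): 90% for both methods, same section.
- Samples: 200 tumor positive and 50 normal (Section 5.4).
- The documents give no AUC value, target or precision, so there is no figure of the plan's own to reproduce.

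**Step 1: area with one interior point.** The empirical ROC joins (0, 0), (1 − Sp, Se) and (1, 1). By the trapezoid rule:

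Area = ½(1 − Sp)Se + ½Sp(Se + 1) = ½(Se − Se·Sp + Se·Sp + Sp) = (Se + Sp)/2.

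The Mann-Whitney form, counting ties as one half, gives the same result:

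Se·Sp + ½[Se(1 − Sp) + (1 − Se)Sp] = (Se + Sp)/2.

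At 90%/90% this is 0.81 + ½(0.09 + 0.09) = 0.90.

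**Step 2: numbers at the planned 200/50 split.** The trapezoid area, the Mann-Whitney area and the simple mean agreed in every table tried.

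| Tumor read positive | Normal read negative | Se | Sp | Area |
|---|---|---|---|---|
| 180/200 | 45/50 | 0.90 | 0.90 | 0.900 |
| 190/200 | 40/50 | 0.95 | 0.80 | 0.875 |
| 170/200 | 48/50 | 0.85 | 0.96 | 0.905 |
| 160/200 | 50/50 | 0.80 | 1.00 | 0.900 |

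The first and last rows describe clearly different tests, with 20 against 40 missed tumor samples and 5 against 0 false positives. They receive the same area.

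**Step 3: what a curve over thresholds could be.** Take the operating point (0.10, 0.90).

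- *Concave curve, lower bound:* the two chords of Step 1, area 0.90.
- *Concave curve, upper bound:* the curve lies below some line of slope s through the point. The triangle left above that line has area ½(0.1 + 0.1s)(0.1 + 0.1/s), smallest at s = 1, where it is ½ × 0.2 × 0.2 = 0.02. The bound is 1 − 0.02 = 0.98.
- *Equal-variance binormal curve (an assumption that is not in the documents):* Φ((1.2816 + 1.2816)/√2) = Φ(1.812) = 0.965.
- *Curve assumed only to be non-decreasing:* from 0.9 × 0.9 = 0.81 up to 0.1 × 0.9 + 0.9 × 1 = 0.99.

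**Step 4: dependence on the definitions.** Step 1 needs Se and Sp conditional on the reference standard, as under step 10 of the study procedure. The Primary Endpoints part of the Analysis Methods words the cCeLL quantities the other way round, conditional on the read, which makes them predictive values. At 90%/90% with 200/50 samples there are 180 + 5 = 185 positive reads and 45 + 20 = 65 negative reads. The values would be 180/185 = 0.973 and 45/65 = 0.692, with mean 0.833. A point plotted from those is not an ROC point, so that wording does not rescue the endpoint. The conflict needs its own correction.

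**The case against.** The strongest reply is that a single operating point is inferred rather than stated. The reference to the results of each endpoint is vague, Section 6.7 has blinded assessments documented for each analyzable image, and secondary endpoint 3 counts the images needed per specimen. A graded sample-level result, such as the share of images read as tumor, could be formed from such data. The reading form is not among the documents, so a rating scale may exist. This stands as a limit on certainty: nobody can say that a graded read is ruled out. But the plan gives no rule that turns image reads into a score, and the scale behind a named endpoint belongs in the protocol. Pooling points from different sites or methods would not give the ROC of one test.

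A second reply is that the AUC is descriptive, drives no test, sample size or success rule, and that its construction is disclosed. All of that is correct and limits the importance of the point.

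A reader might also go further and infer from the binormal figure that the reported value will be 0.965 − 0.90 = 0.065 too low. The documents do not support that. The binormal model is not theirs. Among concave curves the shortfall ranges from 0 to 0.08, and if only monotonicity is assumed even its sign is open. As the mean of sensitivity and specificity, 0.90 is not too low at all; it is a different quantity.

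**Conclusion.** The point holds for the plan as written. With one positive/negative read per sample, and sensitivity and specificity conditional on permanent section, the AUC is (sensitivity + specificity)/2 as an algebraic identity: 0.90 at the plan's anticipated values. It does not measure discrimination across thresholds and adds nothing to the primary estimates. The gap to an AUC over thresholds is unknown; 0.90 to 0.98 is the range under concavity at that operating point. The conclusion rests on no graded score being collected. None is described, and if one exists, specifying it would settle the matter. The consequence is limited to one descriptive secondary endpoint; the primary hypotheses and the sample size are untouched.

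**What to change.** Choose one of two changes.

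**(a) Delete or rename.** Remove secondary endpoint 5 from the Synopsis and Section 8.2, or rename it balanced accuracy, defined as (sensitivity + specificity)/2, and stop using the terms AUC and ROC for it. This is a text edit and needs no new data.

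**(b) Collect a rating.** Add a prespecified ordinal tumor-confidence rating, one per sample, to the cCeLL reading form, and state in Section 8.3 that the ROC and AUC for cCeLL are built from it.

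- Record the rating after the binary tumor/no-tumor call, so that the primary endpoints still rest on that call and need no cut-point on the scale.
- Record it after the reading-time stop, because cCeLL reading time is part of secondary endpoint 1.
- State how samples with unreadable images enter the ROC, since Section 8.3.2 keeps samples analyzable by frozen section whether or not the cCeLL read succeeded.

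Option (b) costs one form field and a protocol amendment, which under Section 9.1 needs REB and Health Canada approval if judged substantial. It requires no extra reader, tissue or procedure. Frozen section would have no matching scale, so the AUC would describe cCeLL only and could not be used to compare the two methods.
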